Prospective, randomized, blinded, controlled, two-arm, parallel clinical trial design with 1:1 allocation ratio to EAA versus Placebo. Staged enrollment is planned; we will complete Aim #1 before enrolling into Aim #2.

Investigational Supplement.

This trial is being conducted under IND#121601, with mandates to report results from Aim #1 to the Food and Drug Administration (FDA). The investigational supplement (or Placebo) will be ingested twice-daily, at 10:00a and 2:00p for one week prior to TKA surgery.

- Aim 1 -Supplement will be compounded by Northwest Compounds, and ordered per standard of care for pharmaceutical ordering (fax or phone call) and dispensing.
- Aim 2 – Supplement will be supplied by MEND Nutrition, Inc. Supplement will come individual containers shipped directly to the [name] Lab. Containers will be distributed to patients by study coordinators. Patient will measure two (2) scoops per dose (twice daily). Scoop provided in each container.

Aim 1 Supplement will be suspended on the day of surgery and resume on post-operative day #1. On post-operative days where subject participates in physical therapy, supplementation will occur within one hour of treatment (20 g of EAA or Placebo). The EAA supplement or Placebo composition is described in Table 1 below. Our preliminary study suggest the EAA supplementation is safe and no subjects withdrew due to problems with supplement ingestion (37).

Aim 2 Supplement will be suspended on the day of surgery and resume on post-operative day #1. On post-operative days where subject participates in physical therapy, supplementation will occur within one hour of treatment (23.42 g of EAA or Placebo). The EAA supplement or Placebo composition provided by MEND Nutrition, Inc. is described in Table 2 below. Our preliminary study suggest the EAA supplementation is safe and no subjects withdrew due to problems with supplement ingestion (37). Supplement composition has changed due to new manufacturer/supplier of the supplement (MEND). To our knowledge there are no scientific or risk implications related to the change in proportions.

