β Aim 1 time point only

Physical Therapy (PT).

Inpatient PT will be standardized for all patients as follows: Post-op day zero (POD#0). Subject will have same-day evaluation if the patient is stable and is transferred to the PT floor by 3:30 pm. POD#1: Patient will have an individual treatment between 9:00 am and 11:00 am and group therapy session at 1:30 pm. POD#2: Patient will have group therapy at 9:30 am and 1:30 pm, and individual treatment. POD#3: 9:30 am exercise class followed by discharge if medically cleared. Supplement will be ingested within 1 hr after morning and afternoon therapy to maximize anabolic effect at each time point (32).

[figure not shown]
[name], PT, and [name] will facilitate standardization of outpatient PT at all locations; however, each patient is individually treated and subjects in EAA may respond/advance through therapy faster, potentially requiring fewer treatments, which would be a positive outcome. This will be accounted for statistically. All subjects will have 14 outpatient therapy visits as follows: Post-op days #5 and #7 for initial evaluation and first treatment. Thereafter PT will routinely see patients 3 times/week for 2 weeks and then 2 times/week for 4 weeks. Physical therapists will be asked to complete a standardized assessment form to document the patient's range of motion, leg circumference and types of exercises performed. The standardized PT data collection tool will be completed by the patient's physical therapist at the first outpatient PT appointment and on the last day treated each week, beginning the week following discharge and ending at post-operative week #5.

For Aim #2, the count of PT visits will be captured as well of date of discharge from formal therapy; however, community therapists will not be asked to complete a standardized assessment. Range of motion at standard of care six week and three month post-op appointment with their surgeon will be obtained.

Aim #1 Study Activities Timeline.

Patients may be enrolled up to six months prior to surgery, and remain on the protocol until 6 weeks ± 2 days post-TKA (up to 7.5 months of total enrollment). Figure 1 (next page) describes the schedule of study-related events, including evaluable time windows, under Study Aim #1.

Figure 1. Overview of Aim #1 timeline and all study activities, measures and procedures.

Schedule of Events									

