**Inpatient Research Protocol & Integration w/ Standard Patient Care: Protocol while subject is inpatient (IP) on orthopedic floor (estimate 2 to 3 days as IP); Daily AM fasting blood draw by phlebotomist on POD 0 and POD 2. (leave blood on ice, research staff to pick up); Subject to don accelerometer at all times; Twice daily ingestion of supplement (subject and investigators are blinded to treatment group); Ingestion will occur 1 hour after daily physical therapy; Inpatient physical therapy to begin at 9 AM and 1 PM. Therapy per MD/PT standard Tx; Twice daily ingestion of deuterium oxide (D₂O); Daily food-log recordings (all nutrient intake) by subject. Research staff and nursing to remind subject to complete this task.

Specific Aim #2 (Physiology).

Aim #2 - Determine if short-term prevention of atrophy, weakness, and functional mobility leads to positive changes in muscle cell structure and function, and quality of life in the long term (6 months post-TKA) vs. Placebo.

Randomization Assignments.

- Aim #2, Trial #1 enrolled 19 patients before closing enrollment in June 2018. Please refer to the Event Form submitted on June 4, 2018 for additional details. Please refer to study protocol December 2017 for information on Aim #2, Trial #1 EAA proportions and protocols.
- Aim #2, Trial #2 (reflected throughout the protocol as "Aim 2") will consist of 2 groups (N=40/group through protocol completion; EAA vs. Placebo) that are identical in protocol design. Up to 160 patients will be consented to achieve 40 per group completion.

Summary of Study-Related Activities.

- Patient questionnaires before and after surgery
- Functional mobility tests before and after surgery
- Accelerometer before surgery and after surgery
- Optional muscle biopsy before and after surgery

Changes to Study-Related Activities.

Omitted Procedures or Measures for Participants Enrolled in Aim #2

- No strength & central activation testing
- No consumption of heavy water (D₂O)
- No muscle biopsies at surgery, 1 week or 2 weeks post-TKA operation
- No blood draws
- No MRIs performed
- No Three day food diary
- Removal of 6 minute walk
- Removal of study questionnaires at 2 weeks post-TKA (functional testing remains)

New or Altered Study Procedures or Measures for Participants Enrolled in Aim #2.

- New study assessment time points: 3 months & 6 months
- Optional (patient choice at enrollment) muscle biopsies at pre-op, 6 weeks & 6 months post-TKA

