
^{*}Twice daily ingestion of supplement (subject and investigators are blinded to treatment group); Ingestion will occur within 1 hour after daily physical therapy.

Participant Withdrawal.

Participants will be withdrawn from the study by the PI or physician Co-Investigators if required to protect the subject's well-being. Adverse events will be closely monitored and assessed for possible relationships to study treatment. Please refer to the *Adverse Event* form, located in Appendix 2. Clear study-stop criteria have been established:

Study Stopping Criteria

Criterion #1: Patient experiences a serious reportable adverse event (SRAE).

1. Death; immediate individual stop.
2. Life-Threatening; immediate individual level stop.
3. Hospitalization (initial or prolonged)
 - a. Where prolonged is defined as discharge on Post-Operative Day 4 (POD #4) or longer; use Criteria #2 to further assess for study stop.
 - b. Where immediate subject withdrawal from study will occur at Post-Operative Day 6 (POD #6)
4. Disability or permanent damage; immediate individual stop.
5. Required intervention to prevent permanent impairment; Use Criteria #2 to further assess.

Criterion #2: The intensity of an adverse event warrants discontinuation at the individual level.

For all adverse events (not limited to SRAEs), grading of severity is derived from the daily life consequences and need for additional treatments/interventions.

[figure not shown]
Intensity of adverse events are defined as follows:

- Mild – Does not interfere with daily activity
- Moderate – Interferes with daily activity, no treatment required
- Severe – Prevents daily activity or requires treatment (see decision support below)
- Life Threatening – Supports stopping decision

Please refer to Figure 3 (next page).

Figure 3. Algorithm for individual-level study discontinuation, essential amino acid versus placebo in TKA.

Algorithm for individual-level study discontinuation.

Criterion #3 – Risk/benefit criteria for individual-level study stop.

Subjects with adverse events will be assessed for risk/benefit stopping criteria.

- Subject experiences clinically relevant deterioration in health (additional adverse events, vital signs, laboratory parameters) following the initial adverse event

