Random coefficients analysis. [name], will run random coefficients analysis (RCA) to model muscle, strength, and functional mobility across time as well as data points generated from accelerometer and functional analysis. RCA models trajectories from assessments nested within subjects (48); tests of condition are represented by the interaction between a time factor and treatment condition. The RCA avoids the many pitfalls associated with traditional repeated measures ANOVA (52, 91, 101). RCA adjusts for within-individual dependence or autocorrelation in the data (48, 91, 108), and with four measurements, the RCA can model nonlinear growth. It does not require fixed spacing among assessments, accommodates missing values over time, and allows piecewise models (i.e., splines) (48). RCA provides a more powerful analysis than ANCOVA. Power estimates of growth models, however, require several assumptions that are not easily established. Thus we rely on the fact that the power for RCA has been shown to surpass that of ANCOVA (53, 86) especially when applied to four or more assessments (118). The RCA, then, will detect smaller differences between conditions than the mixed-model ANCOVA. Finally, optimal Type I error rates do not depend heavily on normally distributed data (48, 52, 74, 85). These methods are also appropriate for relatively small samples, such as those planned for the present study (74).

Missing data. Most longitudinal trials result in missing data. The proposed methods will reduce bias due to missing data (6, 73). Maximum likelihood methods that model time as random, such as RCA, use any available data across time, reducing bias and increasing power (43, 91). Our preliminary data show that we have been successful in collecting >92% of all data points. However, to minimize missing data, the study coordinator and staff will devote significant time and effort to data collection and retention of study subjects.

Potential Limitations.

We do not expect problems with the proposed experimental design or data collection. Our research team has performed every test and used each method included in this proposal. We have identified and addressed issues that may present potential problems and proposed solutions in the Potential Problems and Solutions section of Aim 1. We are well aware of the potential issues related to enrollment goals

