In addition to taking the supplement, we need to test your functional mobility before surgery and after to see how well you can do certain activities. For example, we would ask you to walk as far as you are able for six minutes. You would also be asked to wear a pedometer that measures your level of activity before and after your surgery.

You will be asked to have one muscle biopsy on both legs before your surgery (four to eight weeks), and again six weeks and 6 months after surgery. You may choose to participate in the study without having the biopsies. In addition, if your surgery date is less than 4 weeks away, you may be eligible to participate in the study and complete functional testing and non-biopsy activities only.

A study coordinator from the Slocum Foundation will make sure you understand all the steps and procedures, as well as the risks and potential benefits, involved in the study before you agree to participate.

Has anyone participated in a study like this before?

Yes, Drs. [name], [name] and [name] participated in the pilot data project. The pilot data was published in the Fall of 2013. You can read the study results in the Journal of Clinical Investigation: <http://www.jci.org/articles/view/70160>. In addition, the first part of this new study was completed in 2016. In the new study, 40 patients took the supplement and participated in similar study activities for six weeks after surgery.

What can you tell me about the potential benefits of the study?

Our preliminary studies suggest taking essential amino acid supplements prior to surgery and for two weeks after surgery prevents muscle atrophy. Preventing muscle atrophy is important because improving muscle strength and functional after knee replacement may decrease recovery time; however, this is part of what we are investigating. There is a chance you would receive the placebo (no real supplement), in which case you may not benefit from study participation directly, but you would play an important part in helping us determine whether or not EAA supplementation is beneficial.

Who can I contact to find out more information? You may contact your physician or the Slocum Foundation at [contact] or email [contact].

Informed Consent Process.

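### A stay to post-operative day 6 removes the patient from the study, not only from supplement, before any Aim 2 post-operative outcome; stopping supplement and keeping follow-up costs little.

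*Combined protocol and SAP*

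**What the plan says.** Criterion #1 lists serious reportable events. Under hospitalization, item 3a sends a stay to day 4 or longer to a further assessment under Criterion #2. Item 3b has no such step: "Where immediate subject withdrawal from study will occur at Post-Operative Day 6 (POD #6". It does not repeat that the patient is still in hospital, but its place under that heading makes this the natural reading. The object of the withdrawal is the study, not the supplement.

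The opening of Participant Withdrawal already gives clinicians discretion: "Participants will be withdrawn from the study by the PI or physician Co-Investigators if required" to protect well-being.

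The Aim 2 schedule of events puts the first post-operative functional test at 2 weeks ± 1 week. There is no questionnaire at that visit: "Removal of study questionnaires at 2 weeks post-TKA (functional testing remains". Questionnaires and accelerometer resume at 6 weeks. In Aim 1 the first post-operative functional test is at 2 weeks ± 2 days.

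Under Investigational Supplement, the product "will be ingested twice-daily, at 10:00a and 2:00p for one week prior to TKA surgery", and it resumes on post-operative day 1. The inpatient note to the Aim 1 schedule expects a short stay: "estimate 2 to 3 days as IP".

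Data Analysis specifies ANCOVA with the pretest as covariate, plus random coefficients analysis (RCA). Under Missing data, the plan relies on likelihood methods that, "such as RCA, use any available data across time". The Aim 2 sample size counts completers: 40 per group, with up to 160 patients consented.

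**The concern.** Length of stay is observed after randomisation and after at least a week of supplement, so treatment could affect it. A rule that discards patients because of a long stay is therefore an exclusion on a post-randomisation event. It acts before the first Aim 2 outcome, so the excluded patients have no post-operative functional or questionnaire values.

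If EAA prevents such stays, the placebo arm loses some of its worst recoveries and part of the benefit disappears from the functional contrast. If EAA causes them, the EAA arm loses its worst recoveries and the functional contrast understates the harm. Replacing non-completers until 40 per group finish restores precision but not the randomised comparison.

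The rule applies to both aims, but Aim 1 is over (the Aim 2 website text says "the first part of this new study was completed in 2016"), so only Aim 2 can still be changed. I make no claim about Criterion #1 items 2, 4 or 5, or about Criteria #2 and #3, because the Figure 3 algorithm was not available to me.

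**Working it through.** **Timing.** Earliest Aim 2 post-operative test: 14 − 7 = day 7. Earliest in Aim 1: 14 − 2 = day 12. Withdrawal at day 6 precedes both. In Aim 2 it leaves 0 of 4 post-operative visits (2 weeks, 6 weeks, 3 months, 6 months).

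**The plan's own benchmark.** Power calculations states detectable effects for Aim 2 of 0.79, 0.68 and 0.52 SD (no covariate, r = .50, r = .75) with 40 per group, 85% power and two-sided α = .05. By the normal approximation, (1.960 + 1.036) × √(2/40) = 0.670. By the noncentral t, with the factor √(1 − r²) for the covariate, the values are 0.678, 0.588 and 0.449. The stated figures match about 30 per group (0.787, 0.681, 0.520). They are conservative, and the point does not depend on them. I compare with both sets.

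**Size of the shift.** Let *a* and *b* be the numbers withdrawn at day 6 in the two arms, on top of 40 completers each. Let *D* be how much worse, in SD, these patients would have scored beyond what baseline predicts. Then

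shift = D × [b/(40 + b) − a/(40 + a)].

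The documents give neither the rate nor *D*; all values below are assumptions.

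| Withdrawn (a v b) | Difference, points | D = 0.5 | D = 0.75 | D = 1.0 | D = 1.5 |
|---|---|---|---|---|---|
| 0 v 1 | 1/41 = 2.44 | 0.012 | 0.018 | 0.024 | 0.037 |
| 0 v 2 | 2/42 = 4.76 | 0.024 | 0.036 | 0.048 | 0.071 |
| 1 v 3 | 3/43 − 1/41 = 4.54 | 0.023 | 0.034 | 0.045 | 0.068 |
| 1 v 1, 2 v 2 | 0 | 0 | 0 | 0 | 0 |

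The columns D = 0.5 and 0.75 cover the case where baseline already predicts half of a 1.0 or 1.5 SD deficit.

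- Same number but different type of patient (2 per arm, 1.0 v 1.5 SD worse): 2/42 × 0.5 = 0.024.
- Difference needed for a shift of 0.10 SD: 0.10/1.0 = 10 points, or 0.10/1.5 = 6.7 points.
- Counts of 0 v 2 and 1 v 3 are compatible with chance (Fisher p = .49 and .62). The table gives bias only if the expected difference is caused by treatment; chance imbalance alone is not bias.

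**Can the analysis recover the loss?** I simulated 20,000 trials per setting: 42 randomised per arm, r = .75, one post-operative visit, no EAA effect in other patients.

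| Day 6 rate by arm, D | Everyone followed | Completer ANCOVA |
|---|---|---|
| 0% v 4.8%, 1.0 | 0.048 | 0.000 |
| 0% v 4.8%, 1.5 | about 0.07 | about 0.00 |
| 2.4% v 7.0%, 1.5 | about 0.07 | about 0.00 |
| 5% v 5%, 1.5 | about 0.00 | about 0.00 |

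Completer ANCOVA misses the whole treatment-driven component. A likelihood estimate that keeps the baseline-only patients gives the same answer (0.000 and −0.001 in the first two rows). With equal rates, the completer ANCOVA kept a type I error of about .05. The simulation confirms the formula; it is not evidence that treatment-driven day 6 stays occur.

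**Power.** Precision is hardly affected. If 1%, 2%, 5% or 10% of 80 patients were lost and not replaced, the detectable effect without a covariate would be 0.682, 0.685, 0.697 or 0.716, against 0.678.

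**The case against.** The strongest objection is materiality. No rate is given, no effect of EAA on day 6 stays is shown, and the SD figures return the assumptions put into them. Such stays should be rare: the expected stay is 2 to 3 days, Aim 2 surgery may take place at an ambulatory center, inpatient physical therapy plans for discharge on day 3 if cleared, and patients with significant organ disease or known discharge to a care facility are excluded. All of this stands, and it limits the point to a small improvement.

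Second, safety harm would not go unseen. Prolonged hospitalization is itself a serious reportable event, serious events go to the DSMB and IRBs within 24 hours, and Criterion #4 looks at assignment among affected patients. Admission and discharge dates are collected, and the annual report lists reasons for dropout. This also stands: the harm at issue is in the functional estimate, and what is lost is the outcome data, not every record of the patient.

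Third, with up to 160 consented for 80 completers, general attrition could matter far more than this one trigger. That may be so, but it is no reason to keep an automatic exclusion that can be avoided.

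Fourth, the trial runs under an IND and any change needs IRB approval first, so the cost is more than editing a line. That is fair, though the change leaves the trigger and the clinicians' power to withdraw a patient intact.

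**Conclusion.** The concern holds as a low-cost improvement, not as an error expected to change the conclusion. The text and the timing are clear: item 3b removes the patient from the study, and it does so at least one day before the first possible Aim 2 outcome. Nothing available to me keeps these patients in follow-up, and the planned analyses cannot make up for it.

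The likely effect is small. With a treatment-driven difference of two patients per arm or fewer and a residual deficit of 0.5 to 1.5 SD, the shift is about 0.01 to 0.07 SD. That is well below the stated detectable effects of 0.52 to 0.79 SD and the recomputed 0.45 to 0.68 SD. With equal rates and types of patient it is zero. These figures rest on assumed counts and deficits, and on reading item 3b as applying to patients still in hospital. Confidence is medium.

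**What to change.** Reword item 3b along these lines: at day 6, stop study supplement; continue scheduled functional tests, questionnaires and safety follow-up, omitting any test or biopsy the physician judges unsafe, unless the patient withdraws consent. Keep the day 6 trigger and the discretionary safety withdrawal. Analyse these patients in their randomised arm, and report the number stopped or untestable by arm and reason.

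The cost is a short protocol and consent amendment with IRB approval, plus a few visits. Participant payment is at most 4 × $20 = $80 for a non-biopsy patient, or 2 × $100 = $200 for a biopsy patient's two post-operative biopsies. Much of the structure exists. The adverse event form records action on the study intervention separately. VR-12, Oxford and VAS are standard of care. Surgeon visits also exist: "Range of motion at standard of care six week and three month post-op appointment with their surgeon will be obtained".

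The downsides are slight dilution of the contrast by patients off supplement, and that some of them will still be untestable.
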